Bacterial Wound Contamination Prior to Closure: Povidone-iodine versus Saline Irrigation in Pediatric Spine Fusion Surgery

Version Date: October 16, 2017

Principal Investigator:

*[name]
Assistant Professor, Harvard Medical School
Department of Orthopaedic Surgery
Children's Hospital Boston
[name]
[name]
[contact]*

Co-Investigator:

*[name], MD
Richard M. Armstrong Jr. Professor of Orthopaedic Surgery
Perelman School of Medicine at the University of Pennsylvania
Chief of Orthopaedic Surgery
The Children's Hospital of Philadelphia
[name]
[name]
[contact]*

Co-Investigator:

*[name]
Director, Orthopaedic Research Program
Chair, American Academy of Pediatrics, Section on Orthopaedics
[name] Surgery, University of Missouri-
Kansas City School of Medicine and University of Kansas Medical
Center
Children's Mercy Hospital & Clinics
[name]
[name]
[name]
[contact]*

A. Scientific Aims

The overall goal is to evaluate the safety and efficacy of surgical site irrigation with povidone-iodine in children and young adults undergoing spinal deformity surgery. More specifically, we will: (1) Establish safety of use of dilute povidone-iodine irrigation, (2) Establish baseline tissue colonization prior to closure, (3) Establish bacteriology of tissue contamination prior to closure, (4) Establish population (ie idiopathic vs neuromuscular) specific differences in tissue colonization prior to closure, and (5) Establish estimates for the effect that povidone-iodine/saline have on reducing bacterial contamination.

B. Significance

Due to their profound financial, personal, and societal costs, interventions focusing on preventing post-operative spine infection are of considerable interest.[1-5] The proposed study will hopefully demonstrate that using povidone-iodine irrigation in pediatric spinal patients is safe and reduces bacterial contamination of the spinal surgical wound prior to closure. Following this pilot and assuming there is a reduction in bacterial contamination, we would conduct a multicenter randomized controlled trial (RCT) to assess whether the reduction leads to a lower postoperative spinal infection rate.

C. Background

The rate of wound infection in pediatric and adolescent spine fusion populations has been reported at 0.5-4.3%[4, 6-9] and 8-24% in populations with neuromuscular disease.[4, 10-21] A recent retrospective review of Boston Children's Hospital demonstrated at 10% infection rate in neuromuscular scoliosis over a 3 year period (unpublished data) and a recent multicenter study (unpublished data) demonstrated a 9.2% rate in neuromuscular scoliosis across 3 centers. Based on recent research, we know that there is bacterial contamination of the spinal surgical wound prior to closure. Dietz et al. obtained positive wound cultures in greater than half of patients undergoing clean, elective orthopaedic procedures with no antibiotic prophylaxis.[22] Nandyala and Schwend reported a 23% rate of positive tissue cultures from pediatric patients undergoing posterior spinal fusion, which included a rate of 37% in neuromuscular patients.[23]

Povidone-iodine has long been used topically as a solution to disinfect the skin, and has been used as an intra-operative irrigant for general, cardiothoracic and genitourinary procedures.[24] The standard protocol for irrigation prior to wound closure in spine surgery entails the use of sterile normal saline as an irrigant. Based on its theoretical ability to disinfect the surgical wound prior to closure, two RCTs comparing povidone-iodine to normal saline irrigation prior to wound closure in an adult spine population have demonstrated benefit without complications related to treatment.[25, 26] A recent systematic review on the use of povidone-iodine as a surgical irrigant in adult and pediatric patients concluded that the published studies showed compelling evidence of decreased infection with the use of povidone-iodine, although the level of evidence of these studies was sub-optimal.[27] Based on a number of in vitro and clinical studies, the best available evidence suggests that a concentration of 0.35% is both safe and effective.[27-34]

D. Methods

This will be multi-center, single-blind pilot randomized clinical trial (RCT) comparing povidone-iodine irrigant to normal saline alone.

D.1. Recruitment, Screening and Eligibility

Participating orthopaedic surgeons and the study coordinator will be responsible for case finding and subject recruitment. Patients will be screened and those found eligible will be offered participation. Informed consent will be obtained from the patient or from a parent or legal guardian for patients less than 18 years of age.

D.1.a. Inclusion criteria: Patients must meet all of the following criteria to be *eligible*: (1) Age 3 to 18 years on day of surgery, (2) diagnosis of spinal deformity, (3) undergoing elective posterior spine multi-level instrumentation surgery

D.1.b. Exclusion criteria: Patients having any of these criteria will be *ineligible*: (1) Documented renal failure, (2) documented allergy to iodine or shellfish, (3) previous spine fusion surgery, (4) undergoing elective posterior spine instrumentation surgery fusing fewer than six levels, (5) undergoing anterior or anterior-posterior spine multi-level instrumentation surgery; (6) current antibiotic use.

D.2. Randomization and Blinding

Patients will be randomized to saline or povidone-iodine & saline irrigation via an envelope system. Patients will be blinded to the type of irrigant used. Ideally, surgeons would also be blinded to treatment group; however, it is not possible because they will be irrigating the surgical wound in the operating room and the two solutions will be identifiable because they are a different color.

D.3. Description of Study Treatments

D.3.a. Standardization of Periprocedure interventions

All patients will receive cefazolin (25 to 50 mg/kg, dependent on standard of care) IV within one hour prior to skin incision. Patients will also receive IV gentamycin or tobramycin (2.5 mg/kg) every 8 hours if they have a neuromuscular diagnosis. Appropriate every 3 or 4 hour (according to standard of care) dosing will be continued intraoperatively and for 24 hours post-operatively. If a patient allergy to cefazolin exists, clindamycin dosed every 6 hours or vancomycin dosed every 12 hours may be substituted. Skin will be prepped with chlorhexidine.[24] Surgical approaches, fusion levels, deformity correction techniques, and hardware selection will be at the discretion of the surgeon.

D.3.b. Standardization of Culture/Irrigation Procedure

Prior to closure, a swab or tissue of the surgical wound will be performed (aerobic cultures) to establish the baseline incidence of bacterial contamination. This will be performed by excising the tissue or swabbing the wound under the retractor at the inferior aspect of the wound, using the routine surgical pathology protocol of the institution. Following, any nonviable tissues will be debrided and the irrigant solution (0.35% povidone-iodine or sterile saline) of sufficient volume to fill the wound will be in contact with all areas of the wound for three minutes. A second sample (aerobic cultures) will be collected immediately after lavage with saline or povidone-iodine from the same location to determine reduction in the incidence of bacterial contamination achieved by

each irrigant. This sample will be obtained prior to placement of bone graft/antibiotics to obtain samples as close to closure as possible without allowing the application of local antibiotics to influence the results. A further 2 liters of normal saline will then be used for the povidone-iodine treatment group to irrigate the wound further which will remove traces of the iodine irrigant from the surgical site. If deemed appropriate by surgeon, a patient in the saline treatment group will then be irrigated with povidone-iodine and saline as per standard of care. Use of pulse or low pressure lavage will be up to the discretion of the surgeon.

D.4. Definition of Endpoints

(1) Proportion of patients with an initial positive bacterial culture prior to irrigation (2) Bacteriology of tissue in cases of positive cultures, and (4) Proportion of patients with a positive bacterial culture after irrigation

D.5. Data Collection Methods, Assessments and Schedule

Data will be collected on standardized paper case report forms (CRF) by the study coordinator and entered into a study-specific REDCap database. Study data will be collected at the pre-operative consultation, and during surgery (see Table 1.) Wound cultures will be tested specifically for research to evaluate the efficacy, respectively, of *povidone-iodine*.

Table 1. Schedule of Measurements

Measurement	Baseline (Pre-Operative)	Surgery
Demographics	X	
Medications	X	
Medical history	X	
Laboratory results	X	X
Surgical site cultures (2)		X
Surgery/OR data		X

Demographics, medications, medical history, and laboratory results will be collected from medical records. Surgical data will be collected during the fusion operation and two standard cultures of the surgical site will be taken during the surgery using the routine surgical pathology protocol at each institution. Results from the cultures taken at the fusion operation, in addition to any other associated post-operative cultures, will also be collected post-operatively from medical records.

D.6. Adverse Events and Reporting Procedures

The only foreseeable, but highly unlikely adverse event associated with participation in this trial is an increased level of iodine in the blood as a result of washing the wound site with povidone-iodine. Extra iodine in the body is excreted through urine. A healthy body without thyroid or renal abnormalities is able to excrete excess iodine without any problems.

The monitoring of adverse events will be conducted on an ongoing basis for the duration of the study. If an adverse event occurs, it will be reported immediately to the IRB and the investigators will re-assess the risk/benefit ratio of the study and submit any modifications deemed necessary to the IRB for approval.

D.7. Statistical Considerations

We project an accrual of 150 patients, resulting in 75 per treatment group. Patients will be recruited from “low risk” and “high risk” patient populations in a 3:1 fashion, respectively. “Low risk” patients are defined as those with an idiopathic condition and the “high risk” group will encompass all others. Within each patient “risk” group, randomization will be split evenly between saline and betadine in a 1:1 fashion. Positive cultures before and after irrigation will be monitored to establish the efficacy of povidone-iodine irrigation. 150 patients will provide good statistical precision for estimating the probability of a positive pre-irrigation culture, as shown in the following table. The table shows exact 95% confidence intervals (CI) for the estimated percentage over a plausible range of observed outcomes.

Observed percentage:	30/150=20%	37/150=24.7%	45/150=30%
95% CI:	(14%, 27%)	(18%, 32%)	(23%, 38%)

It will be of interest to examine how the tissue colonization rate varies across subgroups such as neuromuscular and idiopathic patients, which we anticipate to accrue in approximately a 3:7 ratio. Under this assumption, and assuming an overall pre-irrigation colonization rate of 25% and a two-sided $\alpha=.05$ test there will be 69%, 90% and 98% power, respectively, to detect relative risks (RR) of 2.0, 2.5, and 3.0, respectively.

Finally, we expect that the probability of a positive post-irrigation culture in the control group will be about .12, with a further reduction to perhaps .05 in the povidone-iodine group. These results would correspond to a relative risk (RR) of .417. Because positive post-irrigation cultures are projected to be fairly rare events, the size of this pilot study will not provide high statistical power unless the true treatment effect is quite large. However, the study should provide useful preliminary information about the size of the treatment effect. For example, the following table shows the probability that the estimated positive culture rate in the povidone-iodine group that will be at least 4, 5.33, 6.67 or 8 percentage points lower than in the control group, assuming the true control rate is .12 and the true rate in the povidone-iodine group is .05, .04 or .03 (corresponding to RR's of .417, .33 and

.25, respectively. Calculations are based on exact binomial probabilities. Also shown is the power of the study under each set of assumptions, assuming a two-sided $\alpha=.05$ chi-square test.

Number of fewer pos. cultures (of 75) in treatment group.	Observed percentage point reduction	True rates RR		True rates RR		True rates RR	
		.12 vs .05	.417	.12 vs .04	.33	.12 vs .03	.25
≥ 3	$\geq 4\%$ reduction	79%		86%		91%	
≥ 4	$\geq 5.33\%$ reduction	70%		78%		85%	
≥ 5	$\geq 6.67\%$ reduction	58%		67%		76%	
≥ 6	$\geq 8\%$ reduction	47%		54%		65%	
	Power:	33%		43%		55%	

For example (see bolded entry), if the true rates of post-irrigation positive cultures are .12 and .05 in the control and povidone-iodine groups, respectively, corresponding to $RR=.417$, there is a 79% chance that the observed rates will differ by 4 percentage points or more (i.e., 3 or fewer positive cultures out of 75 in the treatment group compared with the number of positive cultures out of 75 in the control group). However, there is only a 33% chance of finding a statistically significant difference (power=33%).

E. Data Management Methods

Every center participating in the trial has a research coordinator on staff that will be responsible for screening and consenting patients, collecting and entering data, and sharing data with the data coordinating center (see paragraph below). Each institution will be given an identifying number, which will be the beginning of each patient's study identification number. Therefore, the patient study identification numbers will be linked to the patients' institution and MRN. Only members of the study group at each institution will have access to the links, which will be destroyed once all of the data is collected.

Access to the REDCap™ database will be set during the creation of the project assigning a password to only members specified in the IRB protocol. As this is a multi-center study, sites will only have access to their own site level data. Boston Children's Hospital, as the coordinating center, will have access to all data. As other investigators or centers join the study, access will be granted only with appropriate IRB approval and they will only have access to their own data.

At the local level, all hard copies of forms that the surgeons or research staff fill out with identifying information on it will be stored in a locked research cabinet in the department and entered into databases only accessible by members of the research staff. A subject's identity on these records will be indicated by a study ID number (a unique identification number created using an algorithm the study administrators will define) rather than by name, and the information linking these study ID numbers with the subjects identity will be separate from the research records and research databases. Only the researchers listed in this protocol will have access to a subject's research records, with the exception of the informed consent form, a copy of which will be kept in the medical record of each subject as this study involves a treatment based protocol. Any information about subjects from this research will be kept confidential as possible.

F. Quality Control Method

The principal investigator will conduct an evaluation of the progress of the research study on a quarterly basis including assessments of data quality and timeliness; participant recruitment, accrual, and retention; and a review of outcome and complication data to determine whether there is any change to the anticipated benefit-to-risk ratio of study participation and whether the study should continue as originally designed, should be changed, or should be terminated. A summary of these reports will be submitted to sites IRBs and to BCH as part of the annual renewal.

G. Data Safety Monitoring Plan

To ensure safety, an independent safety monitor will be appointed to assist with interim data review. The monitor and the study statistician will be completely unblinded to treatment-group-specific results. There will be one scheduled interim analysis, conducted when data from approximately 1/3 and 2/3 of the accrual goal become available. Interim analysis will focus on the comparison of the treatment groups with respect to the primary endpoint, positive culture rate before and after irrigation, using two-sample t-tests. A "stopping rule" using a truncated O'Brien-Fleming procedure will be used to guide the need for further discussion of the possibility of early stopping among a wider group, including the study investigators. (This rule will not be interpreted strictly but rather will be used as a guideline to trigger the need for a wider discussion.) Specifically, the rule is that the stopping boundary is met if the nominal p-value is $p<.001$ at the first look or $p<.0141$ at the 2nd look. The actual O'Brien-Fleming rule would use a nominal p-value boundary of $p<.00052$ at the first look but this is extremely conservative (i.e., it would take an extreme treatment effect to meet this criterion) so the boundary had been truncated to $p<.001$. Along with a criterion of $p<.0451$ at the final analysis, this algorithm ensures an overall type I error of $\alpha=.05$. The stopping rule has a minimal effect on statistical power, less than one percentage point.

In addition to the scheduled interim analysis, the safety monitor will review cases of positive culture results and adverse events. The safety monitor will also review any cases where a patient may require additional testing to follow up on a thyroid or

renal abnormality that develops and advise on whether a wider discussion of early stopping should take place. Such cases will also be reported to the IRB.

H. Project Timeline

We estimate the total time required to complete this study, including recruitment, follow-up and analysis, will be approximately two years.

H. Study Organization

Data collection will be managed by the study coordinator at each site, and overseen by the lead site at Boston Children's Hospital. The Clinical Effectiveness Research Center in the Orthopaedic Surgery department at Boston Children's Hospital will be used as a central location for data management, using REDCap (Research Electronic Data Capture) as the primary receptacle of our data management. REDCap is a software toolset and workflow methodology for electronic collection and management of research and clinical trial data. The REDCap system provides secure, web-based applications that are flexible enough to be used for a variety of types of research, provide an intuitive interface for users to enter data and have real time validation rules (with automated data type and range checks) at the time of entry. These systems offer easy data manipulation with audit trails for reporting, monitoring and querying patient records, and an automated export mechanism to common statistical packages (SPSS, SAS, Stata, R/S-Plus).

REDCap servers are housed in a local data center at Boston Children's Hospital and all web-based information transmission is encrypted. REDCap was developed specifically around HIPAA-Security guidelines. REDCap has been disseminated for use locally at other institutions and currently supports 240+ academic/non-profit consortium partners on six continents and over 26,000 research end-users (www.project-redcap.org).

In addition, data collected will be recorded in such a manner (coded) that subjects will not be identified. The key code and all study documents with coded data (such as case report forms) will be stored in a locked cabinet file and/or password-protected computer file in an access controlled office only accessible to research personnel. Information about study subjects will be kept confidential and managed according to the requirements of the Health Insurance Portability and Accountability Act of 1996 (HIPAA).

H. References

2. Wenzel RP. Health care-associated infections: major issues in the early years of the 21st century. *Clin Infect Dis.* 2007; 45 Suppl 1: S85-8.

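### The time at which the allocation envelope is opened is not stated, so the arm may be known while the baseline sample is taken and the wound is debrided

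*Combined protocol and SAP*

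**What the plan says.** On allocation, section D.2 says only: "Patients will be randomized to saline or povidone-iodine & saline irrigation via an envelope system". The protocol does not say whether the envelopes are opaque, sealed or numbered, who holds them, or when they are opened. Section D.7 adds that allocation is 1:1 within the low-risk and high-risk groups.

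On blinding, D.2 says "Patients will be blinded to the type of irrigant used". For surgeons it says that "it is not possible because they will be irrigating the surgical wound in the operating room and the two solutions will be identifiable" by their colour.

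Section D.3.b gives the order of events. First: "Prior to closure, a swab or tissue of the surgical wound will be performed (aerobic cultures) to establish the baseline incidence of bacterial contamination". The sample may be excised tissue or a swab. The site is fixed, but there is no rule for choosing between the two methods. Next: "Following, any nonviable tissues will be debrided and the irrigant solution" is applied for three minutes. The second sample is taken straight after this, from the same location.

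The first sample supplies endpoint (1) in D.4, and the second supplies the post-irrigation endpoint. Section G names the positive culture rate before and after irrigation as the primary endpoint that is compared between groups at interim analysis.

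**The concern.** The plan's reason for leaving the surgeon unblinded is the colour of the irrigant, and colour can be seen only when the irrigant is brought out. Two steps that can influence the cultures come earlier, and the stated reason covers neither of them.

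- **Baseline sample.** Someone who knows the arm could, without breaching any instruction, choose a swab or tissue accordingly, or sample more or less thoroughly. The pre-irrigation culture would then no longer be protected from knowledge of treatment when it is compared by arm.
- **Debridement.** How much tissue counts as nonviable is a judgement. If it is made more generously in one arm, the post-irrigation culture changes for a reason unrelated to the irrigant.

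Section B makes a reduction in contamination the condition for a multicenter trial with infection as its outcome. The plan provides for recording neither the opening time nor the extent of debridement, so a difference introduced at these steps could not be reliably identified or removed in the analysis.

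**Working it through.** **1. Order of steps against the reason given**

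| Step (D.3.b) | Is colour visible? | Does the plan keep the arm hidden? |
|---|---|---|
| First sample: swab or tissue | No | Not stated |
| Debridement | No | Not stated |
| Irrigation, three minutes | Yes | Not possible (D.2) |
| Second sample | Already seen | Not possible |

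Concealment is compatible with the design for the first two rows, and the plan does not ask for it.

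**2. Inputs, all from D.7**

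75 patients per arm; true post-irrigation rates of .12 (control) and .05 (povidone-iodine); two-sided alpha of .05; chi-square test. Expected positives are 75 × .12 = 9 and 75 × .05 = 3.75, or about 9 against 4.

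**3. Reproducing the plan's own figures**

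Power = Φ{[|p1 − p2| − 1.96 √(2p̄(1 − p̄)/n)] / √(p1(1 − p1)/n + p2(1 − p2)/n)}, with p̄ = .085 and n = 75:

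Φ{[.07 − 1.96 × .04554] / .04518} = Φ(−.426) = 33.5%. The plan states 33%.

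The exact binomial chance of at least 3 fewer positives in the treated arm is Σₐ P(A = a) · P(B ≤ a − 3), where A ~ Bin(75, .12) and B ~ Bin(75, .05). This gives 79.2%. The plan states 79%.

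The plan's figures reproduce, and this point disputes none of them.

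**4. Sensitivity of the estimate to handling**

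The same formula is used with no irrigant effect. The control arm stays at 12%, and handling alone is assumed to move the povidone-iodine arm. These shifts are illustrations and do not come from the documents.

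| Povidone-iodine arm rate | Expected positives of 75 | Chance of at least 3 fewer |
|---|---|---|
| 12% (no shift) | 9 | 26% |
| 10% | 7.5 | 40% |
| 8% | 6 | 55% |
| 6% | 4.5 | 72% |
| 5% (the plan's true effect) | 3.75 | 79% |

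A shift of 1.5 positives in 75 (9 − 7.5) raises the chance of this apparent reduction from 26% to 40%. A shift of 3 raises it to 55%.

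**The case against.** The strongest reply is that silence is not a decision. Opening the envelope just before irrigation fits the wording of D.2, so the plan does not say that the arm is known throughout the operation. That is right. A reader might infer that surgeon blinding has been given up for the whole procedure, and the text does not support this. What stands is that nothing prevents early opening, and that the only reason given for not blinding does not reach the two earlier steps.

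Other parts of the reply also have force:

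- D.3.b is in the passive voice and names nobody as sampler or debrider. That it is the surgeon is a reasonable inference from D.2, not a stated fact.
- D.3.b fixes the sampling site, the order of steps, the contact time and the use of each institution's routine pathology protocol. This narrows the room for differences, but leaves open the choice of swab or tissue and the extent of debridement.
- The choice of lavage ("Use of pulse or low pressure lavage will be up to the discretion of the surgeon") might be read as a third exposed step. The sentence closes the section and is not placed before irrigation. Lavage is also part of irrigating, when the arm is unavoidably known.
- Aim 2, the baseline colonization rate, might seem compromised. D.7 estimates that rate on all 150 patients pooled, so a difference by arm would affect it only through its net effect on the pool. The by-arm baseline matters mainly to the comparison in section G.
- Early opening might seem to let patients be dropped in theatre. No text says that this happens, and D.1 screens for eligibility before participation is offered.
- It is tempting to say that moving one culture per arm makes the result significant. With uncorrected chi-square, 9 vs 4 gives p = .147 and 10 vs 3 gives p = .042. But this needs two shifts in opposite directions. Either one alone gives p = .092 (10 vs 4) or .071 (9 vs 3), and Fisher's exact test on 10 vs 3 gives .078. D.7 already concedes that events are few and power is low. That example therefore does not measure the bias.

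**Conclusion.** The point holds as a gap in allocation concealment that is cheap to close and worth closing. The protocol neither states when the envelope is opened nor protects the first sample and debridement from knowledge of the arm, although both could be protected. The endpoints at risk are the pre-irrigation culture compared by arm and the post-irrigation culture.

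The size of any bias is unknown. With no irrigant effect, the chance of an apparent reduction of at least 3 positives in 75 is 26%. It would be 40% or 55% if handling alone lowered the povidone-iodine arm to 10% or 8%. These figures rest on the plan's 12% control rate, on 75 patients per arm and on the assumed shifts. They show sensitivity, not a predicted bias. The conclusion also assumes that whoever samples and debrides could learn the arm from an opened envelope. The documents establish that possibility and no more.

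**What to change.** In D.2, specify sequentially numbered, opaque, sealed envelopes, in a separate set for each risk group to match the 1:1 allocation within risk group in D.7. In D.2 and D.3.b, state that the envelope is opened only after the first sample has been taken and debridement is complete. Name the role that opens it, and add a CRF field for the opening time so that adherence can be checked.

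The cost is protocol wording and one CRF field. Both irrigants must be ready in theatre until the envelope is opened, with a brief pause at that moment. The sample size of 150, the stated power, the irrigants and the surgeon's choice of lavage do not change.

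### Allocation by an envelope system with no stated safeguard, in a trial whose unblinded surgeons and site coordinators recruit, may let the next arm be foreseen or guessed; central release would close the gap cheaply

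*Combined protocol and SAP*

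**What the plan says.** - **Method (D.2).** "Patients will be randomized to saline or povidone-iodine & saline irrigation via an envelope system". This is the whole description. D.2 adds that patients are blinded but surgeons cannot be, because the two solutions differ in colour.
- **Balance (D.7).** "We project an accrual of 150 patients, resulting in 75 per treatment group", and "Within each patient “risk” group, randomization will be split evenly between saline and betadine in a 1:1 fashion". No block size or other restriction method is given, and site is not named as a stratum.
- **Who recruits (D.1 and E).** "Participating orthopaedic surgeons and the study coordinator will be responsible for case finding and subject recruitment". Section E adds: "Every center participating in the trial has a research coordinator on staff that will be responsible for screening and consenting patients".
- **Central resources (E and Study Organization).** One hospital is the coordinating center and sees all data in REDCap. Each site sees only its own. The documents give REDCap no role in allocation.

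**The concern.** Concealment matters at the moment a patient is offered entry. Here the people who make that offer can learn past assignments. The surgeon sees the irrigant, and nothing says that the coordinator is kept unaware of it. Two routes are open.

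1. **Foreseeing.** With no stated rule on sealing, custody or opening time, the next envelope might be known in advance.
2. **Guessing.** If a site's set is filled evenly, past assignments show which arm is due. Sealing each envelope until surgery does not stop this, because the information comes from earlier patients.

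Either route lets the decision to offer entry, or its timing, depend on the expected arm. The arms could then differ in contamination risk before any irrigation. At stake is Aim 5, the estimated effect on contamination, which section B uses in deciding whether a larger trial follows.

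**Working it through.** **1. Reproduce the plan's figure.** D.7 gives 33% power for .12 versus .05 with 75 per arm (two-sided .05 chi-square). With pooled rate .085:

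- Critical difference: 1.96 × √(2 × .085 × .915 / 75) = .0893.
- Standard error under the alternative: √[(.12 × .88 + .05 × .95) / 75] = .0452.
- z = (.07 − .0893) / .0452 = −.43, so power is 33.5%.

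The stated power is sound. Expected positives are 75 × .12 = 9 and 75 × .05 = 3.75, a gap of 5.25 cultures.

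**2. Group sizes.** D.7 recruits low-risk and high-risk "patient populations in a 3:1 fashion, respectively", so about 112 and 38 of 150. An exact even split is feasible: 56 + 19 = 75 per arm.

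**3. Share of next assignments guessed correctly.** The guesser always names the arm that is behind. In an evenly filled set of 2m with all assignments seen, expected correct guesses are m + 2^(2m−1)/C(2m,m) − 1/2. For a set of 12: 6 + 2048/924 − 0.5 = 7.716, and 7.716/12 = 64.3%.

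| Allocation (all but the first are assumed forms of restriction) | Correct guesses |
|---|---|
| Simple 1:1 | 50% |
| One shared evenly filled list per risk group, three sites, each seeing only its own patients (simulated) | 52.0% |
| The same, in blocks of 4 (simulated) | 52.9% |
| Set of 112, all seen | 55.5% |
| Set of 38, all seen | 58.9% |
| Set of 12, all seen | 64.3% |
| Fixed blocks of 4, all seen | 70.8% |
| Fixed blocks of 2, all seen | 75.0% |

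For the shared list I carry about 52-54%, to allow for block sizes and guessing rules not simulated. The set of 12 is about one site's high-risk group if there are three equal sites (38/3 ≈ 12.7). Both the three sites and separate site sets are assumptions.

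Sets of 112 and 38 together give (62.147 + 22.388)/150 = 56.4%. D.7 also expects neuromuscular and idiopathic patients, "which we anticipate to accrue in approximately a 3:7 ratio". Sets of 104 and 46 on that basis give 56.5%, so the choice hardly matters.

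**4. From guessing to bias.** Let g be the share guessed correctly. Let p1 and p2 be the post-irrigation risks of patients entered when one arm, or the other, is expected. With no treatment effect, the arms differ by (2g − 1)(p1 − p2). For scale, assume .17 versus .07, a 10-point difference around .12:

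| Setting | g | 2g − 1 | Spurious gap (points) |
|---|---|---|---|
| Shared list, three sites | .52-.54 | .04-.08 | 0.4-0.8 |
| Sets of 112 and 38, all seen | .564 | .127 | 1.3 |
| Site sets of 36 and 12 (three equal sites) | .604 | .208 | 2.1 |
| Fixed blocks of 4, all seen | .708 | .417 | 4.2 |

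The effect that D.7 assumes is 7 points.

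**5. Can the pre-irrigation culture reveal it?** At the 25% rate in D.7, the 95% half-width for the between-arm difference is 1.96 × √(2 × .25 × .75 / 75) = 13.9 points. Imbalance of the size above would usually go unseen.

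**The case against.** The strongest reply is that the documents establish a gap in description, not a predictable sequence. Several parts of it stand.

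- **Balance is not stated as exact.** A 1:1 ratio projected to give 75 per arm also fits simple randomization, where guessing stays at 50%. Some restriction is the likelier reading of an even split in a group of about 38, but no more than that.
- **Surgeons do not see every assignment.** A reader might infer this from the lack of blinding. The trial is multi-center, a surgeon sees the patients he or she irrigates, and sites see only their own data. Separate site sets are plausible with physical envelopes but nowhere stated.
- **A large distortion is not shown.** A reader might suppose that selection could easily create a 4-point gap. At g = .604 that needs p1 − p2 = .04/.208 = .19 across all patients. At g = .564 it needs .31, more than the .24 that is possible around a mean of .12. Only small fixed blocks bring it within easy reach, and the plan states none.
- **Motive is weaker than usual.** D.3.b lets a saline patient receive povidone-iodine after the second sample if the surgeon thinks fit.
- **Baseline contamination is measured.** The first culture permits a check and an adjustment. That helps but does not settle the matter: the check is imprecise, adjustment reaches only what one culture captures, and the time at which the arm becomes known is unstated.

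It is also fair that well-kept, sealed and numbered envelopes can conceal. The plan does not describe such a system, and Aims 2 to 4 do not depend on the arm.

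**Conclusion.** The point holds in a limited form. D.2 names an envelope system and no safeguard, while unblinded surgeons and site coordinators recruit. If envelopes are held at sites and arms are balanced within risk group, the next arm may be foreseen, or guessed more often than chance.

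The size cannot be fixed from the documents. The range runs from 50% correct guesses (simple randomization) to 75% (fixed blocks of two), with 55-64% for evenly filled sets of 112 down to 12. On the assumed 10-point difference between favoured and unfavoured entrants, guessing alone gives a spurious gap from under 1 point to about 4 points. Foreseeing an unsealed or open sequence would be worse and is not covered by these figures.

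The gap in the text is certain; confidence in the magnitude is low. The change is still worth making, because the comparison rests on about 13 expected positives (9 + 3.75), selection on unmeasured factors cannot be reliably repaired in analysis, and the means of avoiding it already exist in the trial.

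**What to change.** Replace the envelope sentence in D.2 with text such as:

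> A computer-generated 1:1 allocation list, stratified by risk group and shared across sites, will be held only at the coordinating center. The restriction method will not be disclosed to sites. Each assignment will be released through the study REDCap database only after eligibility and consent have been recorded.

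The gain comes from central custody, release after consent, and a list shared across sites. Varying the block size is not enough by itself: randomly mixed blocks of 4 and 6 still allow about 69% correct guesses if all assignments are seen (simulated), against about 52-54% for a list shared by three sites.

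Cost: a short amendment, a one-time set-up at the existing coordinating center, and a log-in before each case. Final arm sizes may differ slightly from 75, and balance within a site is no longer forced. No patients, visits or procedures are added, and the sample size and stated power stay as they are.
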